5.3.2.3 Dose and Administration

Venetoclax/placebo tablets should be taken orally once daily with a meal and water at approximately the same time each day with ibrutinib capsules. Venetoclax/placebo tablets should be swallowed whole and not chewed, crushed, or broken prior to swallowing. If the subject misses a dose of venetoclax/placebo within 8 hours of the time it is usually taken, the subject should take the missed dose as soon as possible on the same day and resume the normal daily dosing schedule. If a subject misses a venetoclax/placebo dose by more than 8 hours, the subject should not take the missed dose and resume the usual dosing schedule the following day. The use of strong CYP3A inhibitors/inducers, and grapefruit and Seville oranges should be avoided for the duration of the study (Appendix D).

For subjects starting with the concurrent administration of ibrutinib and venetoclax using the standard Ramp-up Schedule, venetoclax/placebo will be delivered in the clinic on Days 1, 2 (all subjects) and 3 (hospitalized subjects) of Weeks 1 and 2; on Days 1 of the remaining weeks during the Ramp-up Period (see Section 8.2); and on the PK sample collection day (see Section 7.1.4.1 and Section 7.1.4.2). Otherwise, venetoclax dosing will be done on an outpatient basis. Subjects should strictly adhere to the Ramp-up Schedule. In the event of TLS, dosing of venetoclax will be withheld and/or modified per the protocol and may be resumed at the investigator's discretion, when all laboratory abnormalities have returned to baseline. If venetoclax is resumed at the same dose level, the 7-day count should be re-started. In cases of vomiting after taking venetoclax/placebo, no additional dose (tablets) should be taken that day. The next dose should be taken at the usual time the following day.

5.3.2.4 Overdose

There is no specific antidote for venetoclax/placebo. For subjects who experience overdose, closely monitor and provide appropriate supportive treatment; during the Ramp-up Period, interrupt venetoclax/placebo and monitor carefully for signs and symptoms of TLS along with other toxicities. Based on the venetoclax (assume for placebo) large volume of distribution and extensive protein binding, dialysis is unlikely to result in significant removal of venetoclax (assume for placebo).

Refer to Section 11.3 for further information regarding special reporting situations as a result of overdose.

5.3.2.5 Dose Modification for Adverse Reactions

Venetoclax/placebo dosing interruption and/or dose reduction may be required. See Table 5 for dose modifications for hematologic and other toxicities related to venetoclax/placebo. For subjects who have had a dosing interruption greater than 1 week during the Ramp-up Period or greater than 2 weeks when at target dose, reassess for risk of TLS to determine if reinitiation with a reduced dose is necessary (eg, all or some levels of the dose Ramp-up Schedule).

Dose reduction of venetoclax is not allowed for subjects enrolled in the Safety Run-in Period (see Section 3.1.1).

Table 5. Recommended Dose Modifications for Venetoclax/placebo-related Toxicities

Event	Occurrence Action		
Tumor Lysis Syndrome			
Blood chemistry changes or symptoms suggestive	Any	Withhold the next day's dose. If resolved within 24-48 hours of last dose, resume at the same dose.	
of TLS		For any blood chemistry changes requiring more than 48 hours to resolve, resume at a reduced dose* (see Table 6)	
		For any events of clinical TLS, resume at a reduced dose following resolution (see Table 6)*	
Non-Hematologic Toxicitie	es		
Grade 3 or 4 non-hematologic toxicities	1 st occurrence	Interrupt venetoclax/placebo Once the toxicity has resolved to Grade 1 or baseline level, venetoclax/placebo therapy may be resumed at the same dose. No dose modification is required.	
	2 nd and subsequent occurrences	Interrupt venetoclax/placebo. Follow dose reduction guidelines in Table 6 when resuming treatment with venetoclax/placebo after resolution. A larger dose reduction may occur at the discretion of the investigator.*	
Hematologic Toxicities			
Grade 3 or 4 neutropenia with infection or fever; or Grade 4 hematologic toxicities (except lymphopenia)	1 st occurrence	Interrupt venetoclax/placebo. To reduce the infection risks associated with neutropenia, granulocyte-colony stimulating factor (G-CSF) may be administered with venetoclax/placebo if clinically indicated. Once the toxicity has resolved to Grade 1 or baseline level, venetoclax/placebo may be resumed at the same dose.	
	2 nd and subsequent occurrence	Interrupt venetoclax/placebo. Consider using G-CSF as clinically indicated. Follow dose reduction guidelines* in Table 6 when resuming venetoclax/placebo after resolution. Additional dose reductions may occur at the discretion of the investigator	

^{*} Dose reduction due to a TLS event or a DLT is not applicable for Safety Run-in Period subjects.

Consider discontinuing venetoclax/placebo for subjects who require dose reductions to less than 100 mg for more than 2 weeks.

If the dose of venetoclax/placebo is reduced, at the investigator's discretion, the dose of venetoclax/placebo may be re-escalated after 2 months of a dose reduction in the absence of a recurrence of the toxicity that led to the reduction. Dose changes must be recorded in the Dose Administration eCRF.

Table 6. Dose Modification for Toxicity During Venetoclax/placebo Treatment

Dose at Interruption	Restart Dose ^a
400 mg	300 mg
300 mg	200 mg
200 mg	100 mg

a Continue the reduced dose for at least 1 week before increasing the dose.

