- Treatment delay of any study drug > 7 days for toxicity

Hematologic DLTs:

- Grade 3 neutropenia is not a DLT; however, Grade 4 neutropenia (ANC < 500/mm³) lasting for > 7 days is a DLT
- Grade 3 or 4 neutropenia complicated by fever ≥ 38.5°C or infection
- Grade 4 thrombocytopenia (< 25,000/mm³) that persists for > 7 days
- Grade 3 or 4 thrombocytopenia associated with Grade 2 or greater bleeding
- Grade 3 anemia is not a DLT; however, Grade 4 anemia is a DLT
- Treatment delay of any study drug > 7 days for hematologic toxicity

Initially, 6 subjects at low risk for TLS and 12 subjects at increased risk for TLS will receive ibrutinib at 560 mg once daily and venetoclax starting at 20 mg and gradually ramped up to a target dose of 400 mg once daily over a 5-week period (see Figure 7 below). TLS events and DLTs will be assessed during the venetoclax Ramp-up Period for a minimum of 5 weeks.

Figure 7. Standard Ramp-up Schedule

Subjects at Low Risk for TLS

Evaluation of TLS

Three additional subjects will be dosed if 1 out of 6 subjects at low risk for TLS experiences a laboratory TLS event and no subjects experience a clinical TLS event. If 0 out of 6 or \leq 1 out of 9 subjects experience a laboratory TLS event and no subjects experience a clinical TLS event, the Randomization Phase will start using the standard Ramp-up Schedule for subjects at low risk for TLS.

If ≥ 2 out of 6-9 subjects at low risk for TLS experience a laboratory TLS event, or any subject experiences a clinical TLS event, the Randomization Phase will start with a 4-week ibrutinib lead-in followed by the standard Ramp-up Schedule (Figure 7) for subjects in both TLS risk categories.

Evaluation of DLTs

With respect to DLTs, if < 2 out of 6 or < 3 out of 9 subjects experience DLT(s) during the DLT assessment period, the Randomization Phase will commence using the standard Ramp-up Schedule for subjects at low risk for TLS (Figure 7). However, if ≥ 3 out of 9 subjects experience DLT(s), the Randomization Phase will commence with a 4-week ibrutinib lead-in followed by the standard Ramp-up Schedule for subjects in both TLS risk categories (Figure 7).

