5.2 Study Treatment

5.2.1 SRI and Randomized Phase

Ibrutinib

• Orally once daily ibrutinib 560 mg (4 x 140 mg capsules OR 1 x 560 mg tablet) continuously

Note: Dose modification of ibrutinib for AEs is specified in Section 5.3.1.4, Section 5.3.1.6, and Section 6.2.1.1.

Important: If using tablets, please ensure that patients do not take more than one 560 mg tablet per day.

Venetoclax

• Orally once daily venetoclax at a target dose of 400 mg (4 X 100 mg)

Note: Dose modification of venetoclax/placebo for AEs is specified in Section 5.3.2.5 and Section 6.2.1.2.

Placebo

• Oral once daily matching placebo for venetoclax at a target dose of 400 mg (4 X 100 mg)

Note: Dose modification of venetoclax/placebo for AEs is specified in Sections 5.3.2.5 and Section 6.2.1.2.

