When resuming treatment, restart at the same or lower dose based on benefit-risk evaluation. If the toxicity reoccurs, reduce daily dose by 140 mg.

^{*} Dose reduction due to a TLS event or a DLT is not applicable for Safety Run-in subjects.

Note: Do not dose below 280 mg daily except in case of required concomitant administration of strong or moderate CYP3A inhibitors or moderate hepatic impairment; refer to Section 5.3.1.6 and Section 6.2.1.

Table 2. Ibrutinib Dose Modifications for Cardiac Failure or Cardiac Arrhythmias

Events	Occurrence	Action	
	First	Hold study drug until recovery to Grade ≤ 1 or baseline; restart at 1 dose level lower (3 capsules [ie, 420 mg daily])	
Grade 2 cardiac failure	Second	Hold study drug until recovery to Grade ≤ 1 or baseline; restart at 1 dose level lower (2 capsules [ie, 280 mg daily])	
	Third	Discontinue study drug	
Grade 3 cardiac	First	Hold study drug until recovery to Grade ≤ 1 or baseline; restart at 1 dose level lower (3 capsules [ie, 420 mg daily]) ^a	
arrhythmias	Second	Discontinue study drug	
Grade 3 or 4 cardiac failure			
Grade 4 cardiac	First	Discontinue study drug	

a Evaluate the benefit-risk before resuming treatment.

Table 3. Ibrutinib Dose Reduction Levels

Starting Dose Level	560 mg
Dose Reduction Level 1	420 mg
Dose Reduction Level 2	280 mg
Dose Reduction Level 3	140 mg
Dose Reduction Level 4	Discontinue

For required dose modification for hepatic impairment refer to Section 5.3.1.6 and for concomitant treatment with CYP3A inhibitors refer to Section 6.2.1.

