6.2.1.2 Concomitant Use with Venetoclax/placebo

Concomitant use of venetoclax/placebo with strong CYP3A inhibitors at initiation and during the Ramp-up Period increases the risk for TLS. Concomitant use of venetoclax/placebo with strong CYP3A inhibitors at initiation (7 days prior to first dose) and during the Ramp-up Period is

contraindicated. For subjects who have completed the Ramp-up Period and are on a steady daily dose of venetoclax/placebo, reduce the venetoclax/placebo dose by at least 75% when strong CYP3A inhibitors must be used concomitantly.

Avoid concomitant use of moderate CYP3A inhibitors with venetoclax. Consider alternative treatments. If a moderate CYP3A inhibitor must be used, reduce the doses of venetoclax/placebo by at least 50%. Monitor subjects more closely for signs of toxicities. Table 7 summarizes the recommended dose modifications with moderate and strong CYP3A inhibitors.

Resume the venetoclax/placebo dose that was used prior to initiating the CYP3A inhibitor 2 to 3 days after discontinuation of the inhibitor.

Avoid concomitant use of venetoclax/placebo with strong CYP3A inducers (eg, carbamazepine, phenytoin, rifampin, St. John's Wort) or moderate CYP3A inducers (eg, bosentan, efavirenz, etravirine, modafinil, nafcillin). Consider alternative treatments with less CYP3A induction.

A list of common CYP3A inhibitors and inducers is provided in Appendix D. For further information, please refer to the current venetoclax IB.

A sample list of cautionary medications that fall into these categories is provided in Appendix D.

Table 7. Management of Potential Ibrutinib and Venetoclax/placebo Interactions with CYP3A Inhibitors

	Venetoclax/placebo		Ibrutinib
Inhibitors	Initiation and Ramp-up Period	Target Daily Dose (After Ramp-up)	At any time
Strong CYP3A inhibitor	Contraindicated	Avoid inhibitor use, consider alternative agent. If must be used, reduce the venetoclax dose by at least 75%	Avoid inhibitor use, consider alternative agent. If must be used, withhold ibrutinib for duration of inhibitor use, or reduce ibrutinib to 140 mg
Moderate CYP3A inhibitor	Avoid inhibitor use, consider alternative agent. If must be used, reduce the venetoclax dose by at least 50%		Avoid inhibitor use, consider alternative agent. If must be used, reduce ibrutinib to 140 mg

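### The bar on venetoclax dose reduction in run-in subjects is broader than its own Table 5 footnote and, read literally, contradicts the CYP3A-inhibitor reductions

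*Protocol*

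**What the plan says.** Section 5.3.2.5 of the protocol states the bar: "Dose reduction of venetoclax is not allowed for subjects enrolled in the Safety Run-in Period (see Section 3.1.1"). The synopsis and Section 3.1.1 carry the same rule, in both cases inside the paragraph on withholding and resuming venetoclax after laboratory TLS.

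The footnote to Table 5, in the same section, is narrower: "Dose reduction due to a TLS event or a DLT is not applicable for Safety Run-in Period subjects". The ibrutinib footnote to Table 1 (Section 5.3.1.4) matches it: "Dose reduction due to a TLS event or a DLT is not applicable for Safety Run-in subjects". The ibrutinib section has no broader sentence beside its footnote.

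Section 5.2.1, which covers both the run-in and the randomized phase, gives the pointer for venetoclax: "Dose modification of venetoclax/placebo for AEs is specified in Section 5.3.2.5 and Section 6.2.1.2". Section 6.2.1.2 then sets the interaction rules. For a moderate inhibitor: "If a moderate CYP3A inhibitor must be used, reduce the doses of venetoclax/placebo by at least 50" percent. For a strong inhibitor, once ramp-up is complete: "reduce the venetoclax/placebo dose by at least 75% when strong CYP3A inhibitors must be used concomitantly". Table 7 repeats both. Neither the section nor the table excepts run-in subjects.

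The paragraph just above the bar in Section 5.3.2.5 has a restart rule that begins: "For subjects who have had a dosing interruption greater than 1 week during the Ramp-up Period". It covers interruptions of more than 2 weeks at target dose as well, and asks for TLS risk to be reassessed to see whether venetoclax should restart at a reduced dose.

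**The concern.** A site with a run-in subject who must take a CYP3A inhibitor finds two instructions. One says cut venetoclax by half or three quarters; the other says no venetoclax reduction for this subject. Nothing in the protocol says which prevails. The case is foreseeable. Section 7.1.4.1, which covers the run-in, requests extra PK samples from subjects who have to start such an inhibitor. Section 6.1 permits antimicrobial prophylaxis, and Appendix D lists ciprofloxacin and fluconazole as moderate inhibitors.

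The same site, faced with a repeated Grade 3 or 4 toxicity late in treatment, finds that Table 5 calls for a step down and the sentence above it forbids one. What is at stake is clear safety dosing for a small open-label group, not an efficacy result.

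**Working it through.** The plan gives no figure on this point, so the check sets the texts side by side, with simple dose arithmetic for scale.

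1. **Who is covered.** The bar attaches to subjects enrolled in the run-in, not to a period. Section 3.1.1 allows up to 27 of them, and Section 5.1.1 keeps them on venetoclax for up to about 104 weeks.

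2. **Against the Table 5 footnote.** The sentence covers every cause; the footnote covers two. This is a difference in scope. Both can be obeyed at once, by never reducing, so it is not a contradiction.

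3. **Against Section 6.2.1.2 and Table 7.** Here the two rules do collide. The dose under the interaction rule is at most (dose) × (1 − minimum cut):
   - strong inhibitor at target dose: 400 × (1 − 0.75) = 100 mg or less;
   - moderate inhibitor at target dose: 400 × (1 − 0.50) = 200 mg or less;
   - moderate inhibitor at the 20, 50, 100 and 200 mg steps: 10, 25, 50 and 100 mg or less.

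   Strong inhibitors are contraindicated in ramp-up, so no strong-inhibitor dose arises there. The literal bar allows no dose below the scheduled one. If venetoclax is given at all alongside the inhibitor, one of the two rules is broken.

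4. **Against Tables 5 and 6 for later toxicity.** Under Section 3.1.1 a DLT is a non-TLS event within the DLT assessment period. SAP Section 2 ends that period on the 7th day at 400 mg, at the earliest Day 4 × 7 + 7 = 35. A related Grade 3 or 4 non-hematologic toxicity after that is not a DLT, so the footnote leaves Table 5 in force: on the second occurrence the dose steps down, for example from 400 to 300 mg. The sentence in the text forbids that step.

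5. **Against the restart rule.** The bar can be read to block restarting at a reduced dose after a long interruption. Adopting the footnote's wording alone would not settle this, because Section 3.1.1 lists as a DLT: "Treatment delay of any study drug > 7 days for toxicity". A ramp-up interruption of more than 1 week for toxicity is therefore itself a DLT, and a lower restart could be called a reduction due to a DLT. The restart rule has to be mentioned by name.

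**The case against.** The strongest reply is that context already answers the question. Section 5.3.2.5 is about adverse reactions, the sentence refers back to a paragraph on laboratory TLS, and both footnotes say TLS event or DLT. CYP3A adjustments are separate, temporary interaction rules: the previous dose is resumed 2 to 3 days after the inhibitor stops. SAP Section 3.4 also treats a venetoclax change for a CYP inhibitor as its own category, with its own check box. Most of this stands, and it establishes the intent. It does not remove the fault, because Section 5.2.1 names 5.3.2.5 and 6.2.1.2 together as the dose-modification sections for adverse events and gives no order of precedence.

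A reader might infer that run-in subjects are forced to take full-dose venetoclax with a strong inhibitor. The documents do not support that. Inhibitors are to be avoided first, and venetoclax can be held or stopped. Holding is only a partial answer in ramp-up, since Sections 5.1.3 and 10.1.1 make a subject non-evaluable after missing 20% or more of planned doses for reasons other than toxicity, and 7 / 35 days = 20%. Table 7 also offers withholding for ibrutinib but not for venetoclax.

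A reader might also infer a loss of protection over the whole 104 weeks. That span measures only the unintended literal reading and says nothing about how many subjects needed a reduction. Nor does any passage class dosing under Table 7 as a protocol deviation.

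The restart limb is the weakest. The restart rule most naturally describes repeating some or all of the ramp-up, which differs from a Table 6 step down.

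**Conclusion.** The point holds as a wording fault. The sentence in the synopsis and Sections 3.1.1 and 5.3.2.5 is wider than the sponsor's own footnote. Read literally, it contradicts the CYP3A reductions that apply to the same subjects, and it bars Table 5/6 reductions for later toxicities that are neither TLS nor DLTs. The intent can be recovered from context, so this is a change that could be made rather than one that must be.

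At most 27 subjects are concerned. The effect is probably mostly in the past: SAP Section 1.1.2 says the ramp-up schedule was already determined in the run-in, SAP Section 4 reports a count from completed randomizations, and planned randomized accrual alone was about 21 months (Protocol Section 10.3) against a 104-week venetoclax course. That is an inference. The documents give no run-in dates, and do not say how many run-in subjects were still on venetoclax or needed an inhibitor.

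A reader might suspect an effect on the PFS comparison. There is none: run-in data are summarized descriptively and separately from the randomized data (Protocol Section 10; SAP Section 2).

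**What to change.** In the synopsis, Section 3.1.1 and Section 5.3.2.5, replace the sentence with:

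> *Dose reduction of venetoclax due to a TLS event or a DLT is not allowed for Safety Run-in subjects. Dose reductions for concomitant CYP3A inhibitors (Section 6.2.1.2) and the TLS risk reassessment before reinitiation after a prolonged interruption (Section 5.3.2.5) still apply.*

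Two further edits are best left out. Ending the bar on the 7th day at 400 mg would misfire for a subject whom a moderate inhibitor keeps at 200 mg or less, because that day would not arrive while the inhibitor continued. Altering the rule that restarts the ramp-up week at the same dose level would change the run-in's test of a fixed schedule, which goes beyond clarification.

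The edit is one replacement text in three places, with no new data and no SAP change. It must still go through a protocol amendment under Section 12.14, with ethics committee and site approval and, if applicable, a revised consent form. It is best carried with the next amendment made for other reasons.

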5.3.2.6 Dose Modification for Hepatic Impaired Subjects

No dose adjustment is recommended in subjects with mild or moderate hepatic impairment based on results of the population pharmacokinetic analysis. A recommended dose has not been determined for subjects who develop severe hepatic impairment.

5.4 Criteria for Permanent Discontinuation of Study Drug

Investigators are encouraged to keep a subject who is experiencing clinical benefit in the study unless significant toxicity puts the subject at risk or routine noncompliance puts the study outcomes at risk. Subjects who discontinue either ibrutinib or venetoclax/placebo (but not both) for tolerability issues may continue in the study as long as they are receiving at least one study drug. For a complete list of criteria for permanent discontinuation of study treatment, refer to Section 9.2.

An End-of-Treatment Visit (Section 8.2.3) is required for all subjects except for those subjects who have withdrawn full consent.

6 CONCOMITANT MEDICATIONS/PROCEDURES

6.1 Permitted Concomitant Medications

Supportive medications in accordance with standard practice (such as for emesis, diarrhea, etc.) are permitted.

Usage of antimicrobial prophylaxis in accordance with standard practice (eg, ASCO guidelines [Flowers 2013]) is permitted and should be considered in patients who are at increased risk for opportunistic infections.

Use of neutrophil growth factors (filgrastim and pegfilgrastim) red blood cell growth factors (erythropoietin) and transfusion is permitted in accordance with institutional policy (eg, ASCO Guidelines [Smith 2006]).

In addition, short courses (\leq 14 days) of steroid treatment for non-cancer related medical reasons (eg, joint inflammation, asthma exacerbation, rash, antiemetic use and infusion reactions) at doses that are clinically indicated are permitted.

6.2 Medications to be Used with Caution

6.2.1 CYP3A Inhibitors/Inducers

6.2.1.1 Concomitant Use with Ibrutinib

Ibrutinib is metabolized primarily by CYP3A4. Avoid concomitant use of systemic strong or moderate CYP3A inhibitors and consider alternative agents with less CYP3A inhibition.

- If a strong CYP3A inhibitor must be used, reduce ibrutinib dose to 140 mg or withhold treatment for the duration of inhibitor use. Subjects should be monitored for signs of ibrutinib toxicity.
- If a moderate CYP3A inhibitor must be used, reduce ibrutinib to 140 mg for the duration of the inhibitor use. Avoid grapefruit and Seville oranges during ibrutinib/placebo treatment, as these contain moderate inhibitors of CYP3A (see Section 6.2.1.1).
- No dose adjustment is required in combination with mild inhibitors.

Table 7 summarizes the recommended dose modifications with moderate and strong CYP3A inhibitors. Avoid concomitant use of systemic strong CYP3A inducers (eg, carbamazepine, rifampin, phenytoin, and St. John's Wort). Consider alternative agents with less CYP3A induction.

A list of common CYP3A inhibitors and inducers is provided in Appendix D. For further information, please refer to the current ibrutinib IB and examples of inhibitors, inducers, and substrates can be found at http://medicine.iupui.edu/clinpharm/ddis/main-table/. This website is continually revised and should be checked frequently for updates.

